3.2.1.3 Handling of Missing or Replicated Data, Unscheduled Visits, and Early Termination Visits

Composite score: NIS score, +7 score, NIS+7 score, modified +7 score, or mNIS+7 score Missing data imputation strategies for missing visit level data

If a patient misses a visit (or the visit is performed outside the analysis visit window), or the entire mNIS+7/NIS+7 assessment is not conducted at a visit, then the mNIS+7/NIS+7 and the composite, components and subcomponents will be considered to be missing at that visit.

Missing data imputation strategies for missing assessment level data

In the parent study, two independent assessments of mNIS+7 are planned at the baseline visit and Week 66 visit, and the early termination visit (for patients that terminate treatment early). A single mNIS+7 assessment is also planned at the Week 35 visit. In this present OLE study, two independent assessments of mNIS+7 are planned at the Week 78 and 156 visit, and the early termination visit for patients that terminate treatment early during years 1 to 3. A single mNIS+7 assessment is also planned at the Week 26, 52, 104 and 130 visit. The mean of the two replicate assessments within visit will be used for analysis of the parent study baseline, the parent study Week 66 visits (provided both visits fall in the visit window and are within 52 days of the last dose of medication), the OLE study Week 78 and 156 visit (provided both visits fall in the visit window and are within 52 days of the last dose of medication). Subcomponent scores will be averaged first. These will be referred to as the averaged subcomponent scores.

At the parent study baseline and Week 66 visit, and the OLE study Weeks 78 and 156 visit, in the event that only one subcomponent has been performed, the single subcomponent will be used in place of the mean value for that visit for the averaged subcomponent score. If both of the subcomponent values are missing, the averaged subcomponent score is missing. At the parent study

and OLE study visits where one assessment is performed, the single subcomponent will be used as the averaged subcomponent score for that visit. These values will be used in the summary of averaged subcomponent scores. The component scores will be computed by summing the averaged subcomponent scores and the composite scores will be computed by summing the component scores.

For both CS2 and CS3, two independent assessments of mNIS+7 are planned at early termination visits. If both assessments are within the same visit window, the mean of the two will be used. At early terminations, in the event that only one subcomponent has been performed, the single subcomponent will be used in place of the mean value for that visit for the averaged subcomponent score.

Imputation of missing averaged subcomponents

If a patient has completed at least part of the mNIS+7/NIS+7 at a visit then the following imputation method will be used to impute this missing assessment level data for the purposes of determining component scores for summary and analysis.

The following missing data imputation steps will be considered and will be used as described below for Groups A, B, and C:

- Step 1: If at least 50% of averaged subcomponent scores within a component are available, the
 missing averaged subcomponent scores will be set to equal to the mean of the patient's other
 non-missing averaged subcomponent scores in that component. The component score is then
 calculated.
- Step 2 (Parent study baseline): In the unlikely event that there are more than 50% of the averaged subcomponents scores within a component that are missing at baseline, the missing averaged subcomponent scores will be set to equal to mean baseline averaged subcomponent score from the parent study Randomized Set (across treatment groups). The component score is then calculated. This is the same definition as used in the parent study.
- Step 3 (OLE study baseline and CS2 and CS3 post-baseline visits): For certain components, and
 only under certain conditions which will be listed below, the missing averaged subcomponent
 scores at that visit within that component only will be set equal to the mean averaged
 subcomponent score among the subjects randomized to placebo in the parent study in the
 Randomized and Enrolled set for CS2 and CS3 respectively. The component score is then
 calculated. This is the same definition as used in the parent study for post-baseline visits.

If a post-baseline assessment does not fall into the scheduled analysis windows, there is no obvious visit on which the mean subcomponent scores in the placebo group can be derived. In order to apply step 3, the following visits will be used to derive the mean scores in the placebo group:

Timing of Assessment	Visit used for deriving the mean subcomponent scores in	
	the placebo group*	

Before Week 26	OLE baseline
Between Week 26 and Week 52	Week 26
Between Week 52 and Week 78	Week 52
Between Week 78 and Week 104	Week 78
Between Week 104 and Week 130	Week 104
Between Week 130 and Week 156	Week 130
After Week 156	Week 156

^{*}Note: the Placebo group refers to the group of patients randomized to placebo in the parent study in the Enrolled set for CS3.

The components of the mNIS+7 and NIS+7 are grouped into A, B and C based on the imputation step used, as follows. A detailed list of components by group can be found in Table 1–Table 3 in Appendix 1 Components and Subcomponents of the mNIS+7, and NIS+7:

 Group A: For components with multiple subcomponents except the NCT component of +7, imputation step 1 and 2 will be applied.

If, after applying step 1 for post-baseline visits, 6 out of the 7 components of the mNIS+7 composite score (NIS-C, NIS-R, NIS-S, NIS-W, HP, TP or NCT) are available and only one is missing at that visit, then step 3 will be applied for the missing component.

If, after applying step 1 for post-baseline visits, 4 out of the 5 components of the NIS+7 composite score (NIS-C, NIS-R, NIS-S, NIS-W, or NCT) are available and only one is missing at that visit, then step 3 will be applied for that the missing component.

Mean averaged subcomponent score used in the imputation described in step 3 are derived from the averaged subcomponent scores before step 1 imputation among the group of patients who were randomized to placebo in the parent study.

If, after applying steps 1-3 as appropriate, there are still missing subcomponent scores, the component score will be set to missing.

• Group B: For the NCT component of +7, it should be noted that the following 3 of the 5 subcomponents of this component may be "not evaluable" as an additional category to missing: 1) fibular nerve motor conduction velocity (PMCVK), 2) fibular nerve distal latency (PMLA), 3) tibial nerve distal latency (TMLA) (see Table 3 in Appendix 1 Components and Subcomponents of the mNIS+7, and NIS+7). These nerve conduction attributes are not evaluable when the tibial or fibular nerve amplitude is 0, therefore, these "not evaluable" results are considered informative missing results and a slightly different imputation method is applied here. The following imputation rule will be used for Nerve Conduction Tests component score of +7: The normal deviate score for PMCVK, PMLA and TMLA will be respectively set to 3.72 (the worse response)

if the recorded response was classified "not evaluable." After this, imputation step 1 and 2 will be applied.

If, after applying step 1 for post-baseline visits, 4 out of the 5 components of the NIS+7 composite score (NIS-C, NIS-R, NIS-S, NIS-W, or NCT) are available and only one is missing at that visit, then step 3 will be applied for that the missing component.

Mean averaged subcomponent score used in the imputation described in step 3 are derived from the averaged subcomponent scores before step 1 imputation among the group of patients who were randomized to placebo in the parent study.

Note that these components are *not* used in the nerve conduction component of the *modified* +7, therefore Group B only includes the NCT component of the NIS+7 and not the NCT component of the mNIS+7.

- Group C: The two components, HRDB and vibration tests, have only one subcomponent. Missing data for these averaged subcomponents score will be imputed as follows:
 - For Parent study baseline, the missing averaged subcomponent scores will be set to equal
 to the mean baseline averaged subcomponent score from the parent study Randomized Set
 (across treatment groups). This is the same definition as used in the parent study.
 - o For OLE study baseline and CS2 and CS3 post-baseline visits, the missing averaged subcomponent scores at that visit will be set equal to the mean averaged subcomponent score among the subjects randomized to placebo in the parent study in the Randomized and Enrolled set for CS2 and CS3 respectively. If a post-baseline assessment does not fall into the scheduled analysis windows, there is no obvious visit on which the mean subcomponent scores in the placebo group can be derived. In order to derive the mean scores in the placebo group, the following visits will be used:

Timing of Assessment	Visit used for deriving the mean subcomponent scores in the placebo group*
Before Week 26	OLE baseline
Between Week 26 and Week 52	Week 26
Between Week 52 and Week 78	Week 52
Between Week 78 and Week 104	Week 78
Between Week 104 and Week 130	Week 104
Between Week 130 and Week 156	Week 130
After Week 156	Week 156

^{*}Note: the Placebo group refers to the group of patients randomized to placebo in the parent study in the Enrolled set for CS3.

Composite Score

The composite scores of mNIS+7, NIS+7, modified +7, +7, and NIS will each be calculated by summing the imputed components scores. If any of the component scores after imputation is still missing within a composite, the composite score will be set as missing.

Norfolk QOL-DN Domain and Total score

- For each patient at a specific visit (defined by the analysis visit window), if at least 50% of the questions for a domain (physical functioning/large fiber neuropathy, activities of daily living, symptoms, small fiber neuropathy) are not missing or if at least one question is not missing for autonomic domain, the missing questions are imputed as follows:
 - For the Parent study baseline, if any question is missing at baseline, the mean value for this question at baseline from the parent study Randomized Set (across treatment groups) will be used to impute the missing baseline question value, i.e., same with the derivation in the parent study. For the symptom domain, in the case that a patient responded on a particular question (Questions 1-7) as not a having the symptom but also marked presence of the symptom in their feet, legs, hands, or arm, the question will be set to missing and the imputation rules will be followed.
 - o For the OLE study baseline and post-baseline visits: any missing question values will be imputed using the last observed or imputed question value (including parent study baseline value). For the symptom domain, in the case that a patient responded on a particular question (Questions 1-7) as not a having the symptom but also marked presence of the symptom in their feet, legs, hands, or arm, the question will be set to missing and the imputation rules will be followed.
 - o Otherwise, the total for that domain will be set to missing.

The Norfolk QOL-DN total score will be calculated by summing the imputed domain scores. If any domain score after imputation is still missing, then the Norfolk QOL-DN total score will be set to missing.

The Norfolk QOL-DN individual domain and total scores will only be calculated for visits where the patient had a Norfolk QOL-DN assessment. The individual domain and total scores are set to be missing if a patient misses the visit or does not have a Norfolk QOL-DN assessment at that visit.

NSC Domain and Total score

In the parent study, two independent assessments of NSC are planned at the baseline visit and the Week 66 visit. A single NSC assessment is planned at the Week 35 visit. In this present OLE study, two independent assessments of NSC are planned at the Week 78 and 156 visit. A single NSC assessment is planned at the Week 26, 52, 104 and 130 visit. The mean of the two replicate assessments within a visit will be used for analysis of the parent study baseline, the parent study Week 66 visits (provided both visits fall in the visit window and are within 52 days of the last dose of medication), the OLE study Week 78 and 156 visit (provided both visits fall in the visit window and

are within 52 days of the last dose of medication). The individual questions scores will be averaged first. These will be referred to as the averaged question scores.

At the parent study baseline and Week 66 visits and the OLE study Weeks 78 and 156 visit, in the event that only one question has been performed, the single question will be used in place of the mean value for that visit for the averaged question score. If both of the questions are missing, the averaged question score is missing. At the parent study Week 35 visit, the OLE study Week 26, 52, 104 and 130 visit only one assessment is performed, therefore the single question will be used as the averaged question score for that visit. The sub-domain and domain scores will be computed using the averaged question scores

Imputing Missing Assessment averaged question Scores

The following imputation rule will be applied at the domain level for the sensory (hypo / loss of sensation), sensory (paresthesia, hyper sensation), autonomic (GI and urinary incontinence), and autonomic (other than GI/urinary incontinence) domains

- If at least 50% of the averaged question scores in the domain are available, the missing questions will be set to be equal to the mean of the non-missing averaged question scores in the domain. The total domain score is then calculated from the sum of the non-missing and imputed averaged question scores in the domain
- Otherwise, the domain score will be considered to be missing

Note for the imputation of the autonomic (other than GI/urinary incontinence) component in women, questions 35 and 36 are ignored and are not included in the imputation procedure

The following imputation rule will be applied at the sub-domain level for the four muscle weakness sub-domains (head and neck, chest, upper limb, lower limb):

- If at least 50% the averaged question scores in the sub-domain are available, the missing averaged question scores will be set to be equal to the mean of the non-missing questions in the sub-domain. The total sub-domain score is then calculated from the sum of the non-missing and imputed averaged question scores in the sub-domain
- Otherwise, the sub-domain score will be considered to be missing

The total value for the muscle weakness domain score is calculated by summing the four sub-domain scores. If one or more of the sub-domain scores is missing, the muscle weakness domain score will be missing.

The total NSC score is calculated by summing the 5 domain scores. If one or more of the domain scores is missing the total NSC score will be missing.

Imputation of Missing/Partial Dates The imputation of partial or missing dates for adverse events and concomitant medications are detailed in Section 3.3.1. The imputations of partial or missing dates for duration of disease from diagnosis and duration from onset of symptoms for FAP/FAC are detailed in Section 3.2.3.

Replicated Data, Unscheduled Visits, and Early Termination Visits

When change from baseline is assessed at a post-baseline visit, unless otherwise specified, only patients with both baseline and post-baseline measurements will be included in the analyses. If baseline or post-baseline value is missing for a patient, then the change from baseline will be set to missing.

For patients who withdraw from the OLE study, all data will be reported prior to the point of withdrawal in line with the population definitions and the specified analysis.

For data that are scheduled to be measured in duplicate or triplicate, the mean value of the patient will be used in tables and figures, while all measured values will appear in the listings.

If more than the scheduled number of measurements is taken, the mean will include all replicate measurements.

Analysis Visit Windows

- The efficacy and PD data will be assigned to a visit according to the visit windows in the table 1 of Appendix 3 Analysis Visit Windows. Because mNIS+7 may be implemented over several days, window definitions are based on the study day the assessment was initiated. Efficacy assessments (except BMI and mBMI) that occurred more than 52 days after the last dose of Study Drug in either parent study or the OLE study will not be included in the efficacy analysis/summaries during the efficacy on-treatment period, even if they occurred within one of the visit windows. PD assessments, as well as BMI and mBMI, that occurred more than 28 days after the last dose of Study Drug in either parent study or the OLE study will not be included in the PD analyses/summaries during the PD on-treatment period, even if they occurred within one of the visit windows. For patients who have multiple visits within a window the visit nearest the target day will be used unless two visits are equally near, in which case the average will be used. Note that if there are multiple visits within a window with some being from the posttreatment evaluation period of either the parent study or the OLE study, the visits from the post-treatment evaluation period will not be used. For mNIS+7 at baseline and Week 66 of the parent study or at Week 78 and 156 of the OLE study, the two assessments are averaged (provided both assessments are within the visit window and are within 52 days of the last dose of medication).
- Efficacy and PD data collected during the post-treatment period will be summarized with
 respect to the elapsed time from last dose. Assessments will be slotted into follow-up visit
 windows according to elapsed time from last dose based on the scheduled assessments during
 the post-treatment evaluation period of the study. The planned windows for this investigation
 are shown in the table 2 of Appendix 3 Analysis Visit Windows.
- Visit based safety assessments (scheduled and unscheduled) will be assigned to a visit according to analysis visit windows in the table 3 of Appendix 3 Analysis Visit Windows, even if they occurred within one of the visit windows. Except for platelet assessments from the local laboratory, local laboratory assessment will not be assigned to a visit and the nominal visit only will be presented in the listings. Safety assessments that occurred during the safety post-treatment period (i.e., more than 7 days after the last dose of study drug) will not be included in

the visit based safety analyses during the safety treatment period. If there are multiple visits within a window, the visit nearest the target day will be used unless two visits are equally near, in which case the average will be used. Note that safety assessments that are not utilized in the visit based summary tables will appear in listings and be used in the determination of treatment-emergent shifts or abnormalities.

• To assess the impact of treatment discontinuation on safety parameters, data from visit based safety assessment in the post treatment phase may also be summarized with respect to the elapsed time from last dose. Assessment will be slotted into follow-up visit windows according to elapsed time from last dose based on the scheduled assessments during the post-treatment evaluation period of the study. The planned windows for this investigation are shown in the table 4 of Appendix 3 Analysis Visit Windows.

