3.2.1.2 Scoring of Assessment Instruments

mNIS+7

The mNIS+7 consists of two composite scores: the NIS composite score (maximum of 244 points) and the modified +7 composite score (maximum of 102.32 points).

NIS

The NIS composite score consists of 4 components:

- Cranial Nerves (NIS-C), maximum 40 points
- Muscle Weakness (NIS-W), maximum 152 points
- Reflexes (NIS-R), maximum 20 points
- Sensation (NIS-S), maximum 32 points.

Questions that make up each composite are listed in the table below.

NIS composite	Question number
Cranial Nerves	1-5
Muscle Weakness	6-24
Reflexes	25-29
Sensation	30-37

Note that each question is separately assessed for the right and left side of the body, meaning that questionnaire is comprised of 74 subcomponents (37 for the left side, and 37 for the right side).

Modified +7

The modified +7 composite score consists of 4 components:

- 1 component for autonomic nerve assessment:
 - Heart Rate to Deep Breathing (HRDB), minimum -3.72 points, maximum 3.72 points,
- 1 component for the nerve conduction assessment of the lower and upper limbs:
 - \circ Nerve Conduction Tests (Σ 5 NC), maximum 18.6 points from 5 subcomponents (PMAK, TMAK, UMAE, USAW, SSAB) with minimum -3.72 points and maximum +3.72 points each,
- 2 components for the sensory nerve assessment:
 - o Touch-Pressure (TP), maximum 40 points
 - Heat-Pain (HP), maximum 40 points.
 NOTE: Testing for both TP and HP is done at up to 10 sites on one side of the body. To obtain the full body score for TP and HP, the summation scores from all 10 anatomical sites

is multiplied by 2 (only one side of the body is tested as FAP is symmetrical neuropathy, identical results are assumed for the other side).

Component	Data entry convention /Comment	Pre-processingstep
Heart Rate Deep Breathing	If HRDB could not be measured due to pacemaker or arrhythmia, MC Core checked either the box "no reliable data to due pacemaker" or "no reliable measure points due to arrhythmia," and left the HRDB score as blank in the BioClinica database	None
	If HRDB was not measured in error or missing for other reasons, MC Core entered a "-9" into the BioClinica database	Set "-9" to missing
	Transform normaldeviate score so that larger values coincide with worse outcomes	Multiply subcomponent score by "-1"
Nerve conduction test	If the nerve attribute was not tested in error, MCCore entered a "-9" into the BioClinica database	Set "-9" to missing

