3.4.2.2 Additional Efficacy Analysis on the Change from the OLE Study baseline

The following additional analysis will be done for mNIS+7 score:

 Responder Analysis for mNIS+7 score described in section 3.4.2.1 based on the change in mNIS+7 score from the OLE study baseline will be performed. The efficacy analyses described in this section will be repeated using the OLE study PPS.

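### Imputing a missing mNIS+7 component at the OLE baseline from placebo patients can create false improvement in former-active patients; never-measurable HRDB gets a change made only of other patients' data

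*Combined protocol and SAP*

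**What the plan says.** SAP 3.2.1.3 imputes in a fixed order. Step 1, which opens "If at least 50% of averaged subcomponent scores within a component are available, the", fills gaps from the patient's own other items in the component. Step 3 opens "Step 3 (OLE study baseline and CS2 and CS3 post-baseline visits): For certain components, and" and then assigns the mean "subcomponent score among the subjects randomized to placebo in the parent study", with donors from the "Randomized and Enrolled set for CS2 and CS3 respectively". For the multi-item mNIS+7 components (Group A), Step 3 is used only if a single one of them still lacks a score after Step 1; the condition begins "6 out of the 7 components of the mNIS+7 composite score (NIS-C, NIS-R, NIS-S, NIS-W, HP, TP or NCT) are available and only one is". A wholly missed assessment is not imputed.

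HRDB has a single item and falls in Group C, where neither Step 1 nor the 6-of-7 condition operates. A value missing at the parent baseline takes the mean of the whole parent Randomized Set. After that the rule is "For OLE study baseline and CS2 and CS3 post-baseline visits, the missing averaged subcomponent scores at that visit will be set equal" to the placebo-group mean. SAP 3.2.1.2 foresees such gaps: "If HRDB could not be measured due to pacemaker or arrhythmia", the core facility leaves the score blank.

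Under SAP 3.2.1.1.2 the mNIS+7 OLE baseline is the average of the two parent Week 66 assessments when these are the last available. Change from that baseline is summarised under SAP 3.4.1. Under SAP 3.4.2.2 a responder analysis on the change in "mNIS+7 score from the OLE study baseline will be performed". SAP 9.1 removes neither output. SAP 9.2.1 adds a statistical analysis of change from the CS2 baseline.

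**The concern.** The SAP justifies Step 3 as the definition already used for post-baseline visits in the parent study. There, giving an active patient the placebo mean counts against the drug. In the extension, the same Week 66 value becomes the baseline. Higher scores are worse, so too high a baseline makes later change look like improvement and makes it easier to meet a responder threshold.

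The HRDB rule raises a different problem. A patient with a pacemaker or persistent arrhythmia may never contribute an HRDB value, yet the composite cannot be formed without one, so Group C supplies it at every visit. The donors change between the parent baseline and later visits. The patient's HRDB change is therefore not the patient's own, and it enters change from the CS2 baseline as well as change from the OLE baseline.

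**Working it through.** **Inputs from the documents.** Donor group and scope: SAP 3.2.1.3. Source of the OLE baseline: SAP 3.2.1.1.2. Expected direction: Protocol 2.2 predicts that the drug will slow or halt progression, so placebo is expected to be worse at Week 66; no figure is given. HRDB range: -3.72 to 3.72 (SAP 3.2.1.2). The documents state no bias figure, so there is none to reproduce.

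**Scale check.** NIS: 40 + 152 + 20 + 32 = 244. Modified +7: 3.72 + 18.6 + 40 + 40 = 102.32. Total 346.32, as in SAP 3.4.2.

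**Bias for one component in a former-active patient.** Let A0 and A1 be the true former-active means at the OLE baseline and at a later visit, and P0 and P1 the former-placebo means. Put D0 = P0 - A0 and D1 = P1 - A1. The true change is A1 - A0.

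- Missing at the OLE baseline only: (A1 - P0) - (A1 - A0) = -D0.
- Missing at the visit only: (P1 - A0) - (A1 - A0) = +D1.
- Missing at both: (P1 - P0) - (A1 - A0) = D1 - D0.

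With an assumed D0 of 2 points:

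| D1 | Baseline only | Visit only | Both |
|---|---|---|---|
| 2 (gap unchanged) | -2 | +2 | 0 |
| 1 (gap halved) | -2 | +1 | -1 |
| 0 (gap closed) | -2 | 0 | -2 |

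**Group mean, baseline-only case.** If a share f of former-active patients is affected, the bias is -f × D0. Both inputs are assumptions: f from 2% to 20%, D0 from 0.5 to 10 points.

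- Lowest: 0.02 × 0.5 gives -0.01 point.
- Middle: 0.05 × 2 gives -0.1; 0.10 × 10 gives -1.0.
- Highest: 0.20 × 10 gives -2.0 points.

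The top of the range is generous: 10 points exceeds the whole HRDB range and is more than half the nerve-conduction maximum of 18.6.

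**Single patients.** The imputed baseline is too high on average, not in every patient. If own values are normal, the placebo mean is worse than the patient's own value with probability 0.50, 0.58, 0.69 or 0.84 for D0/SD of 0, 0.2, 0.5 or 1.0.

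**HRDB never measurable.** Let M be the all-patient mean at the parent baseline and Pt the placebo-group mean at visit t. The recorded change from the CS2 baseline is Pt - M, and no term comes from the patient. If HRDB donors follow the planned 90:45 allocation (an assumption), M = (2Ab + Pb)/3, where Ab and Pb are the arm means at the parent baseline, and

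Pt - M = (Pt - Pb) + (2/3)(Pb - Ab).

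So it contains the placebo group's change plus a baseline difference between arms. From Week 66 to the CS3 visits the donors can also switch from randomized placebo patients to those enrolled in CS3, which alone can produce change. HRDB can move the composite by at most 2 × 3.72 = 7.44 points, or 7.44/346.32 = 2.15% of the scale.

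**The case against.** A reader might infer that the rule pushes former-active patients toward improvement throughout the extension. The documents do not support that. On the same premise, a component missing only at an OLE visit makes the patient look worse. Such gaps may be the more common ones: Weeks 26, 52, 104 and 130 have one assessment, whereas Week 66 has two and either suffices. For multi-item components, Step 1 and the 6-of-7 condition narrow the rule further. All of this stands and limits the size of the effect. It does not remove the baseline-only case, and for HRDB the replicate helps only when the gap is accidental.

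Nor does the effect reach all efficacy results. The study has no formal hypotheses (SAP 1.3). The CS2-baseline analysis does not use the OLE baseline, and the integrated summaries use the ISIS 420915 baseline, which for former-active patients is the parent baseline. Degree of progression, which started from Week 66, is dropped. The responder analysis spans nine thresholds, so no conclusion rests on one. This too stands for the OLE-baseline mechanism. It does not answer the HRDB point, which enters change from the CS2 baseline.

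Two HRDB readings also go too far. The SAP does not say that a pacemaker or arrhythmia makes HRDB missing for good, so the point is confined to patients in whom it is never measured. And the recorded change is not simply the placebo group's change, because the parent-baseline donor is the whole Randomized Set.

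Finally, using own-arm means at every CS3 visit would, if placebo is worse, lower former-active imputed scores and flatter change from the CS2 baseline. That objection is sound, and the fix below avoids it.

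**Conclusion.** The concern holds in a limited form. For a former-active patient with a component missing at the OLE baseline and observed later, change from the OLE baseline and the responder analysis on it are biased toward improvement, on average by the Week 66 arm gap in that component. This rests on placebo being worse at Week 66, which the protocol predicts but does not quantify. The size is unknown; the group-mean range of -0.01 to -2.0 points depends wholly on assumed rates and gaps. With gaps at OLE visits the bias reverses, and with gaps at both ends it is the difference between the two gaps.

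The HRDB point does not depend on which arm is worse. A never-measurable HRDB acquires a change made of other patients' data and changes of donor set, bounded by 7.44 points, in analyses from either baseline.

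There is also an ambiguity to settle. The Step 3 heading names the OLE baseline, but the Group A and B text invokes Step 3 for post-baseline visits, and the donor set for the OLE baseline is not stated outright.

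**What to change.** 1. When computing change from the OLE baseline, impute a component missing there with the mean of the patient's own parent-study arm at that visit, and say explicitly that this replaces Step 3 and Group C at the OLE baseline. Leave the rule unchanged at CS2 and CS3 post-baseline visits. In the algebra above, the baseline-only bias becomes zero on average if the gaps are unrelated to the patient's score within arm; the visit-only case stays +D1; the both-missing case becomes +D1, toward worsening if D1 is positive.
2. For patients whose HRDB is unmeasurable at all visits because of pacemaker or arrhythmia, use one constant imputed value at every visit, so that HRDB adds nothing to change. The all-patient parent-baseline mean already in the SAP would serve.
3. Report the number of Step 3 and Group C imputations by arm and visit, with a sensitivity analysis without them. Composites lacking a component would then be missing, as SAP 3.2.1.3 already provides.

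Cost: SAP wording and a small amount of programming. In the few affected patients, Week 66 shown as a CS2 visit may differ from the value used as the OLE baseline; a footnote should say so.
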